3 OBJECTIVES

11
12
13

3.1 Study Objectives

14
15 Conduct a Phase 1 study to document safety and tolerability of *Lactobacillus reuteri*
16 17938 in children 2-24 months of age.

17
18
19

3.2 Study Outcome Measures

20
21
22

3.2.1 Primary Outcome Measures

23
24 There are three major areas of safety and tolerability that will be assessed in this phase I
25 trial. The outcome measurements will be compared between the two treatment groups
(Intervention v placebo) with intent to treat analysis.

26
27
28 **1. Evidence of invasive infection resulting from the administration of *L. reuteri* DSM
29 17938.** Baseline and daily temperature measurements will be made during the study
30 period. Complete hemogram with differential count obtained at baseline, on day 5, and
31 on day 28. Vital signs will be monitored daily during the administration of the treatment
32 (days 1-5). The evaluation of all febrile episodes will be done and include a physician
33 exam and the evaluation of blood smears for malaria and blood cultures for the
34 evaluation of possible bacteremia.

35
36 Specific outcome parameters in this category include:

37
38 a. Mean daily temperature
39 b. Incidence of fever on study days 1-5
40 c. Frequency of temperature readings categorized as fever (adjusted for number of
41 subjects per group)
42 d. Number of episodes of *L. reuteri* bacteremia

43
44 **2. Clinical tolerance.** The inclusion of a placebo group will allow for comparisons of daily
45 symptom measurements to be compared between the treatment and placebo group.
The symptoms will be monitored for at household visits, and will be graded as
adverse events according to defined criteria. Symptoms monitored as AEs include
fever, nausea/upset stomach, vomiting, diarrhea, irritability, rash, pruritis, and
wheezing or bronchospasm. Diagnostic microbiology will be performed on all stool
specimens from subjects who develop diarrhea during the 90 days following initiation
of therapy.

46
47 Specific outcome parameters in this category include:

- 1 a. Frequency and severity of symptoms monitored as AEs (adjusted for number of
2 subjects per group)
- 3 b. Frequency of all AEs (adjusted for number of subjects per group)
- 4 c. Frequency of SAEs (adjusted for number of subjects per group)

5

6

7 **3. Evidence of toxicity resulting from the *L. reuteri* DSM 17938 preparation.**

8 Participants will have baseline, day 5, and day 28 assessment of hematologic status and
9 renal and hepatic function. Assessment of renal function will include blood urea nitrogen
10 (BUN) and creatinine (Cr). Assessment of hepatic toxicity will include transaminases
11 (AST, ALT) and total bilirubin. Hematologic status will be determined by CBC to measure
12 hemoglobin and absolute leucocyte count, as mentioned above.

13 Specific outcome parameters in this category include:

14

15

16 a. Mean values for laboratory tests monitored (adjusted for number of subjects per
17 group). These are listed in Appendix D.

18 b. Frequency of out of range values for laboratory tests monitored (adjusted for number
19 of subjects per group). These are listed in Appendix D.

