5 STUDY ENROLLMENT AND WITHDRAWAL

1

2 **5.1 Subject Inclusion Criteria**

3

4

5 In order to be eligible to participate in this study, a subject must meet all of the following
6 criteria:

7

- 8 • Have a parental permission form signed by both parents
- 9 • Be between 8 weeks to 24 months of age with no preexisting exclusion criteria
- 10 • Have parents who are willing to comply with all planned study procedures and be available for planned study visits for 3 months.

1
2 **5.2 Subject Exclusion Criteria**

3
4 1) No enrollment of family members in households where any of the following are
5 present:
6
7 a. Another study participant in the household
8
9 b. Presence of immune suppressed individuals or use of immunosuppressive
10 agents (including but not limited to corticosteroids, methotrexate, etc.) by any
11 household member
12
13 c. Presence of a serious congenital anomaly or chronic medical condition that in
14 the opinion of the investigators would contraindicate participation in any household
15 member, including history of gastrointestinal surgery, chronic gastrointestinal
16 illness, abnormal intestinal anatomy, or abnormal bowel functionality
17

18 The following risk factors are at the level of the individual child:

19
20 2) Allergy to penicillin, cephalosporins, clindamycin or gentamicin
21 3) History of antibiotic use in the last 30 days
22 4) Use of probiotic products within the past 30 days, including masato (local
23 product with fermenting bacteria) and yogurt products containing live
24 bacterial cultures.
25 5) History of diarrheal illness within the past 30 days (See definition in Protocol
26 Appendix B)
27 6) Presence of fever or a pre-existing adverse event monitored in the study
28 (See Protocol Appendix B Definitions of AEs for specific adverse events
29 monitored in the study)
30 7) Positive results on serum diagnostic tests for antibodies to HIV.
31
32 8) Presence of severe anemia, defined as serum hemoglobin \leq 7 gm/dL
33
34 9) Out of range laboratory values for total leucocyte count, BUN, Creatinine,
35 AST, ALT, and total bilirubin monitored as potential adverse events, as
36 described in Appendix E.
37 10) Pre-enrollment stool sample (collected within 14 days of day 1 of the study)
38 is positive for *L. reuteri* by PCR.
39
40

1 **5.3 Strategies for Recruitment and Retention**

2 The community where recruitment will occur has been a research site for the current

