7.3 Screening

1
2 1) The screening period may take up to 14 days, all days are categorized as D0 (day 0).
3 repeat measures of biochemistry and hematology will be allowed in a one month time
4 frame.
5
6 2) If the participant meets all criteria that do not require blood tests and both parents sign
7 the informed consent, basic demographic data and clinical data, including use of
8 medications and use of herbal or homeopathic treatments, will be recorded. A stool
9 specimen will then be collected to test for presence of *L. reuteri* by PCR per Laboratory
10 SOP (xxx). Potential participants must not currently be experiencing any of the monitored
11 clinical adverse events as specified in Protocol Appendix C (Clinical adverse events to be
12 monitored).
13
14 3) Following this step, blood will be collected for baseline (day 0) CBC, AST, ALT, total
15 bilirubin, creatinine and BUN. Blood collection may be done by fingerstick, heelstick, or
16 venipuncture, with method based on subject and parent/guardian preference and
17 technical considerations. A total volume of 1.5 milliliters of blood is the minimum required
18 volume to perform all of the assays listed above and a sample volume of 3.0 ml is the goal
19 to ensure specimen adequacy for primary safety outcomes. Due to the time required for
20 testing, reporting, and review of stool PCR and lab tests that would potentially exclude a
21 participant, results of stool PCR and blood tests listed above from specimens collected
22 within 14 days of initiating study product will be used as Day 0 blood and stool results.
23 Out of range laboratory values detected by Day 0 blood test results will be documented on
24 a CRF, and potential subjects will be excluded if an out of range laboratory value for tests
25 monitored as potential adverse events is found, as described in Toxicity Table (Protocol
26 Appendix E, based on Day 0 blood test results. However, subjects will only be excluded
27 based on serum hemoglobin if they meet exclusion criterion 8.
28
29 4) Participants with no laboratory exclusion criteria (from *L. reuteri* stool PCR, HIV,
30 leucocyte count, severe anemia, AST, ALT, T. bili, BUN, creatinine) will have a
31 standardized history and physical examination performed by a physician. Results of
32 serum hemoglobin (exclusion criterion #8) and HIV serum antibody (exclusion criterion #7)
33 will be reported as promptly as possible, usually within 48 hours, to determine if

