9.2 Methods and Timing for Assessing, Recording, and Analyzing Safety Parameters

9.2.1 Adverse Events

Adverse Event: ICH E6 defines an AE as any untoward medical occurrence in a patient or clinical investigation subject administered a pharmaceutical product regardless of its causal relationship to the study treatment. An AE can therefore be any unfavorable and unintended sign (including an abnormal laboratory finding), symptom, or disease temporally associated with the use of study product including active or placebo.

1
2 According to the U.S. DHHS Common Rule an AE **does** include any:

3
4

- exacerbation of a pre-existing illness, such as asthma.
- increase in frequency or intensity of a pre-existing episodic event or condition.
- condition detected or diagnosed after study product administration even though it may have been present prior to the start of the study.
- continuous persistent disease or symptoms present at baseline that worsen following the start of the study.
- symptoms associated with disease not previously reported by the subject will be recorded as an AE.

12
13 According to the U.S. DHHS Common Rule

14 (<http://www.hhs.gov/ohrp/policy/advevntguid.html>) an AE **does not** include a/an:

15

- medical or surgical procedure (eg, surgery, circumcision, transfusion); the condition that leads to the procedure is an AE.
- pre-existing diseases or conditions present or detected at the start of the study that do not worsen.
- situations where an untoward medical occurrence has not occurred (eg, hospitalization for elective surgery, social and/or convenience admissions).

21
22 All AEs including local and systemic reactions not meeting the criteria for “serious
23 adverse events” (See Section 9.2.2) will be captured on the ADVERSE EVENT CRF.
24 Information to be collected includes event description, time of onset, clinician’s (MD)
25 assessment of severity, relationship to study product and time of
26 resolution/stabilization of the event. All AEs occurring while on study product or within
27 90 days of follow-up must be documented appropriately regardless of relationship to the
28 study product. All AEs will be followed to adequate resolution.

29
30 Any medical condition that is present at the time that the subject is screened will be
31 considered as baseline and not reported as an AE. However, if it deteriorates at any
32 time during the study, it will be recorded as an AE.

33

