- provision of additional information about newly recognized risks to previously enrolled subjects.

Some incidents, experiences, and outcomes that occur during the conduct of human subjects research represent unanticipated problems but are not considered adverse events. These may involve social or economic harm instead of the physical or psychological harm associated with adverse events. In other cases, unanticipated problems place subjects or others at increased risk of harm, but no harm occurs. Unanticipated problems must be reported, even if they do not involve adverse events. However, adverse events that do not meet the criteria to be considered unanticipated problems are not subject to these reporting requirements.

Incidents or events that meet the OHRP criteria for unanticipated problems involving risks to subjects or others require the completion of an AE report form.

Additional reporting requirements. Abuse or illegal activities will be reported to Peruvian authorities in a manner consistent with local laws. A written note, documenting the concern, and witnessed of reported behavior giving rise to the concern, is issued to the Peruvian community designated “Defensor de Pueblo” the local legal authority that investigates cases of child abuse and exploitation.

9.2.4 Procedures to be Followed in the Event of Abnormal Laboratory Test Values or Abnormal Clinical Findings

Baseline lab tests will be reviewed by the study physician as part of the screening process. In order to be eligible to participate in the study, all monitored baseline laboratory values must be within the normal range for the reference laboratory.

1 Laboratory values provided by the clinical laboratory that are not among the group of
2 monitored laboratory tests do not have to be within the normal range in order for a
3 consented subject to become a participant, but these reportedly abnormal values will
4 be noted on the FORM FOR EVALUTION OF LABORATORY VALUES. These non-
5 monitored laboratory values provided as part of the complete blood count (CBC)
6 include platelet count and percentage of various leukocyte categories in the differential.
7 Monitored laboratory values are:

8

- 9 • Hemoglobin
- 10 • Total leukocyte count
- 11 • Total serum bilirubin
- 12 • Blood urea nitrogen (BUN)
- 13 • Creatinine
- 14 • Alanine transaminase (ALT)
- 15 • Aspartate aminotransferase (AST)

16

17 Monitored laboratory values will be reviewed by the study physician within 48 hours of

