18 receiving the report from the reference laboratory, and values will be recorded on the
19 appropriate CRF (FORM FOR EVALUATION OF LABORATORY VALUES). Abnormal
20 values meeting toxicity level 1 or 2 which do not warrant further clinical investigation will
21 be noted as such on the laboratory values CRF along with an assessment of
22 relationship to the study product. These abnormal values will be reported to the
23 oversight agencies as AEs according to procedures described below. Abnormal
24 values meeting toxicity level 1 or 2 which may, in the judgment of the study physician,
25 warrant further investigation will result in a clinic visit for full evaluation recorded on the
26 ADVERSE EVENT CRF and will be followed to completion and resolution as with other
27 AEs. Abnormal values meeting toxicity levels 3 or 4 will be considered SAEs and will
28 be evaluated, monitored, and reported according to procedures described for SAEs.

29

30 **Documenting AEs**

31 Any AE occurring during the study must be documented in the subject's medical records
32 and on the appropriate AE CRF, i.e. the AE Report Form. Information to be collected on
33 the AE Report Form includes event description, time of onset, investigator assessment of
34 severity, and relationship to the study product, time of resolution of the event, seriousness,
35 and outcome. All adverse events occurring during the study must be documented
36 appropriately regardless to the relationship of the event with study participation.

37

38 The investigator or study physician should attempt to establish a diagnosis of the event
39 based on signs, symptoms, and/or other clinical information. A diagnosis, if known, or
40 clinical signs and symptoms if diagnosis is unknown, rather than the clinically significant
41 abnormal laboratory finding, should be completed on AE CRF form. If no diagnosis is
42 known and clinical signs and symptoms are not present, then the abnormal finding should
43 be recorded. The laboratory data should either be recorded on the AE forms with the
44 reference range and baseline value(s) or copies of the laboratory reports and reference
45 ranges should be sent with the CRF pages.

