16 treatment group. The normal range for each parameter will be used to create categories
17 of low, normal, or high. Any result higher than the upper limit normal (ULN) will be
18 categorized as high, any result lower than the lower limit of normal (LLN) will be
19 categorized as low, and any result within the LLN and ULN will be categorized as normal.
20 The number and percentage of subjects in each shift category from baseline to final
21 evaluation will be shown for each parameter. Only the hematology and blood chemistry
22 tests with a numeric normal range and at least one follow-up value will be analyzed for
23 shifts from baseline. The number and percentage of subjects with clinically significant
24 values will be presented.

25
26 **B. The secondary outcome measurements** are

27
28 1. To determine the duration of shedding of *L. reuteri* DSM 17938 following controlled
29 administration.

30
31 Since the longitudinal nature of the repeated PCR assays results in correlated outcomes,
32 generalized estimating equations (GEE) will be used to model the binary response
33 whether subjects exhibited a positive PCR result during the various period of study. The
34 duration of shedding of *L. reuteri* will be assessed using Kaplan Meier Product limit
35 estimates.

36
37
38
39
40 **11.2 Sample Size Considerations**

1
2
3 The sample size for this Phase 1 safety trial in healthy children aged 2-24 months is
4 determined by historical precedent for safety in human use.

5
6 Enrollment for the prior Phase 1 studies in adults (Safety of LR in Healthy volunteers
7 #NCT00774163) and children (Safety of LR in healthy children 2 to 5 years of age in Peru
8 #NCT02124122) have been able to recruit and retain >95 subject (Phase 1 child study in
9 progress). We have high and similar rates of retention in our other studies with more
10 complexity and participant burden, even among our birth cohorts.³⁷

11
12 Missing data will not be imputed. Data will be analyzed per treatment group assignment
13 after the administration of a single dose of product for all safety and tolerability analyses.
14 Data regarding the duration of carriage will be restricted to those individuals who complete
15 5 days of therapy.

16
17 The amount of subjects in this study will likely be underpowered to detect differences in
18 most secondary outcomes. This is in part due to the lack of information on key

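### Children may enter with low hemoglobin, but primary outcome 3b has no baseline condition and the three-category shift table cannot show existing anemia worsening; 9.2.4 also contradicts the entry rule

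*Combined protocol and SAP*

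**What the plan says.** **Entry.** Section 5.2, item 8, excludes for "Presence of severe anemia, defined as serum hemoglobin" of 7 g/dL or less. Item 9 begins "Out of range laboratory values for total leucocyte count, BUN, Creatinine" and goes on to AST, ALT and total bilirubin; hemoglobin is not in it. Section 7.3, item 3, makes the exception explicit: subjects are excluded only "based on serum hemoglobin if they meet exclusion criterion 8". Section 7.5 plans iron for children below 11 g/dL (9.5 at 5 months or younger) at baseline or day 5, so it expects some to enter low. Section 9.2.4 says the opposite: "all monitored baseline laboratory values must be within the normal range for the reference laboratory". Its list of monitored values starts with hemoglobin.

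**Outcome 3b** (3.2.1, repeated in 11.1) is "Frequency of out of range values for laboratory tests monitored (adjusted for number" of subjects per group). It covers the Appendix D tests, which include hemoglobin. Group size is the only adjustment.

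**Shift table** (11.1). Results are classed against the normal range. Anything under the lower limit is "categorized as low, and any result within the LLN and ULN will be categorized as normal". The comparison runs from baseline to final evaluation.

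**Adverse events.** Section 9.2.4 sends level 1-2 laboratory values to the "oversight agencies as AEs according to procedures described below. Abnormal" (the last word opens the next sentence). It sets no baseline condition. Section 9.2.1 says a condition present at screening is "considered as baseline and not reported as an AE. However, if it deteriorates at any" time, it is recorded. The treatment-emergent definition in 11.1 also counts pre-existing events only when they worsen.

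**The concern.** For six of the seven monitored tests, entry requires a normal value, so an out-of-range follow-up value is a new finding. Hemoglobin is the exception under 5.2 and 7.3: a low value on day 5 or 28 may simply be the entry value again. Outcome 3b does not separate the two cases, yet 3.2.1 says it is compared between arms, and 9.6 puts out-of-range values by group before the DSMB.

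Two things are at stake. A difference between arms in 3b could reflect which arm happened to enroll more anemic children, and a real product effect on hemoglobin would be diluted by prevalent cases. In addition, the one table meant to show movement between categories cannot show an already anemic child getting worse.

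**Working it through.** The plan gives no figure to reproduce here. Section 11.2 bases the 60 children on historical precedent, and 2:1 allocation gives 40 active and 20 placebo.

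**1. Who can enter out of range (5.2 item 8 with Appendix D).**
- 6-24 months, normal from 11: above 7.0 to 10.9 g/dL.
- 2-5 months, normal from 9.5: above 7.0 to 9.4 g/dL.

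**2. Values that 3b collects with no change in any child.** Prevalence p of low hemoglobin at entry is not in the documents, so 20 to 70% is assumed. If those children stay low at both draws, the count is 60 × p × 2: 24 at 20%, 36 at 30%, 60 at 50%, 84 at 70%. These are totals over both arms. They show how much prevalent anemia can enter 3b, not a difference between arms.

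**3. Chance imbalance.** Let A ~ Binomial(40, p) and P ~ Binomial(20, p) be the numbers low at entry. The SD of the difference in proportions is √[p(1−p)(1/40 + 1/20)]. The last column is the exact probability that |A/40 − P/20| ≥ 0.20.

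| p | Expected low, active / placebo | SD of difference | Probability of 20 points or more |
|---|---|---|---|
| 20% | 8 / 4 | 0.110 | 8.6% |
| 30% | 12 / 6 | 0.125 | 13.5% |
| 50% | 20 / 10 | 0.137 | 17.1% |
| 70% | 28 / 14 | 0.125 | 13.5% |

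**4. Dilution (illustration only).** Assume a new or worsened low hemoglobin in 30% of active and 5% of placebo children, whatever their baseline, and assume children low at entry stay low. Per child, the out-of-range proportion is p + (1−p)w, where w is the arm's rate, so the difference is (1−p) × 25 points. At p = 20% this is 0.44 versus 0.24. Power is for a two-sided Fisher test at 0.05, also assumed, because the plan names no test.

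| Count | Difference | Power |
|---|---|---|
| Baseline-referenced | 25 points | 64% |
| All out of range, p = 20% | 20 points | 27% |
| p = 30% | 17.5 points | 19% |
| p = 50% | 12.5 points | 13% |
| p = 70% | 7.5 points | 8% |

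**5. Shift table against Appendix D grades.**

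| Age | Baseline → final, g/dL | Shift table | Grade | Change |
|---|---|---|---|---|
| 6-24 months | 10.9 → 7.1 | low → low | 1 → 2 | −3.8 |
| 6-24 months | 7.1 → 6.5 | low → low | 2 → 3 | −0.6 |
| 6-24 months | 9.9 → 7.0 | low → low | 2 → 2 | −2.9 |
| 2-5 months | 9.4 → 7.1 | low → low | 1 → 2 | −2.3 |

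The third row shows that grade shifts alone also miss a large fall within Grade 2.

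**The case against.** The strongest reply is that other parts of the plan do use baseline. Section 11.1 summarizes hematology at baseline and change from baseline by group. The shift table separates normal to low from low to low, so new anemia can be told from prevalent anemia. Grade 3-4 values are SAEs. Section 7.5 says iron will be controlled for in the laboratory outcomes. All this stands, and it rules out the reading that the plan cannot see an anemic child worsen. What remains is narrower. Group summaries can hide individual falls, a Grade 1 to 2 fall is not an SAE by grade, and the method of controlling for iron is not stated. Iron started 5 days after a last dose on day 5 would begin on day 10, so it can also affect day 28 values and make the stable counts in step 2 too high.

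A reader might also infer that the same stable value will be an AE in some DSMB tables and not in others. The documents do not support this. The closed-session AE summaries are treatment-emergent, and 9.2.1 already sets the baseline rule. What is left is an unqualified sentence in 9.2.4. I could not check the opening part of 9.3, to which 9.2.4 points for AE reporting procedures.

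Finally, if the 9.2.4 eligibility sentence governs, no child enters low and the mixing in 3b disappears. This is correct, but 5.2, 7.3 and 7.5 all point the other way.

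**Conclusion.** The point holds in limited form. The entry passages contradict each other. If low hemoglobin is allowed at entry, 3b as worded mixes baseline anemia with new toxicity, and the shift table cannot separate stable from worsening anemia.

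Randomization rules out systematic bias; the harm is chance imbalance and dilution with 20 placebo children. An imbalance of 20 points or more has a probability of about 9 to 17% at the four assumed prevalences. The dilution figures rest on assumed event rates as well.

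One might be tempted to say that the toxicity outcome mostly measures anemia at enrollment. The documents do not support this: it depends on a prevalence they do not give, and the toxicity category also contains outcome 3a, the mean laboratory values. This is a worthwhile, inexpensive improvement to a primary safety outcome, not a flaw that undermines the trial.

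**What to change.** 1. Reconcile the eligibility sentence in 9.2.4 with 5.2 (items 8 and 9), 7.3 (item 3) and 7.5. Which rule applies is for the sponsor and investigators to decide.
2. If low hemoglobin is allowed at entry, amend 3b in 3.2.1 and 11.1 for hemoglobin. Report, by arm, the number of children with a follow-up value that is newly out of range or at least one Appendix D grade worse than their own baseline. Show the raw out-of-range count beside the baseline count.
3. In 11.1, tabulate hemoglobin shifts by Appendix D grade, 0 to 4. Keep the change-from-baseline summary so that falls within a grade, such as 9.9 to 7.0, stay visible.
4. Align the 9.2.4 sentence on level 1-2 values with the 9.2.1 baseline rule. Do not define AEs by a worse grade alone: that would drop the 9.9 to 7.0 fall, which 9.2.1 captures as a deterioration.

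The cost is wording in three sections and one re-categorized table, with no new data. The small downside is that hemoglobin is tabulated differently from the other laboratory tests.
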